9.15 Interruption and withdrawal of subjects from clinical investigation

A patient will be discontinued prematurely from the study if they do not complete the last protocol-scheduled follow-up visit due to any of the following causes:

- the patient withdraws consent to participate in the study;
- one of the inclusion criteria will be dropped or an exclusion criterion will occur;
- lack of response to treatment that generates an unacceptable risk for the patient and prevents the continuation of the treatment covered by this observational scientific research;
- onset of a serious adverse event that generates an unacceptable risk for the patient and prevents the continuation of treatment;
- the patient does not follow the procedures of the clinical protocol provided by his doctor;
- decision of the Investigator in the interest of the patient;
- patient no longer available (lost to follow-up);
- death of the patient during the study period.

Patients who are prematurely discontinued will be reported in the data collection form through the appropriate discontinuation visit. The Investigator will have the obligation to report to the Sponsor the patients who are prematurely discontinued and, if the patient is not assessable, or is discontinued before the end of the treatment period for supposed recovery scheduled for the control visit at the third month after the operation), may agree with the Sponsor on the replacement of the patient according to the following procedure.

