9.4 Endpoint

In the present Clinical Investigation, the two variables chosen as *the primary and secondary endpoints* to measure the primary and secondary objectives of the Survey also coincide with the measures of response to treatment, in particular:

- Primary endpoint (security measure):

the safety of the *Chimaera* will be measured by the percentage of patients who within a 6-month observation period, due to serious adverse events related to *the Chimaera*, will have to undergo a second operation to continue with the treatment of the proximal femur fracture.

- Secondary endpoint (efficacy measure):

the effectiveness of the treatment carried out with *Chimaera* will be measured through the Bowers & Parker functional score for the evaluation of the patient's functional recovery.

Note:

Bowers & Parker's functional score⁷ It is a validated and unanimously recognized reliable score for the evaluation of patients treated following a hip fracture. This score assesses the patient's functional recovery (in terms of pain, walking ability and social independence) compared to the patient's condition before the fracture. The Bowers & Parker score also has predictive value for assessing the long-term mortality of the treated patient, and for planning short-term rehabilitation activities.

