9.6 Patients selection

An adult patient with a previously untreated proximal femoral fracture who, in the Investigator's sole judgement, has an appropriate indication for surgical treatment with Chimaera will be considered eligible for the Clinical Investigation. Patients who meet all of the following inclusion criteria and none of the exclusion criteria will qualify for enrolment in this Clinical Investigation.

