9.6.1 Inclusion criteria

A patient will be considered eligible for participation if:

- directly or indirectly (through a legally acceptable representative), he/she has expressed the willingness to participate in the Investigation by signing and dating the informed consent form;
- he/she is at least 65 years of age at the time of signing the informed consent form;
- he/she has been diagnosed with a stable or unstable fracture in the pectrochanteric, intertrochanteric, or subtrochanteric region of the femur, not previously treated;
- in the opinion of the Investigator, he/she has a standard indication for surgical treatment with an intramedullary nail;
- the fracture will be treated with the short (length = 180 mm) Chimaera nail and one or two telescopic cephalic screws, in accordance with the manufacturer's instructions for use.

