9.6.2 Exclusion criteria

A patient will be considered not eligible for participation if:

- he/she is undergoing surgery to address the sequelae of a previously treated fracture;
- he/she has been diagnosed with a pathological fracture of oncologic origin (primary tumour or skeletal metastasis);
- he/she has been diagnosed with a fracture in the diaphyseal and/or distal region of the femur;
- he/she has been diagnosed with an open proximal femoral fracture (type II or III according to the Gustilo and Anderson classification);
- he/she has been diagnosed with multiple fractures (including bilateral proximal femoral fractures);
- during the preoperative or intraoperative phase, it is decided to treat the fracture with the long version of the Chimaera nail and/or with non-telescopic (fixed-length) cephalic screws;
- he/she has a medical condition that constitutes a contraindication to treatment with Chimaera according to the manufacturer's instructions for use;
- he/she has a suspected or confirmed hypersensitivity/allergy to any component of the device that comes into contact with the patient;
- he/she presents with any clinical condition that, in the opinion of the Investigator, could interfere with the Clinical Investigation procedures or compromise patient safety;
- he/she is concomitantly treated with a non-permitted device that cannot be removed without compromising patient safety;
- he/she is participating in another clinical study or has participated in another clinical study within 3 months prior to signing the informed consent form.

9.7 *Expected Number of Patients to be Enrolled*

Considering the high proportion (approximately 25%) of anticipated premature withdrawals in this patient population, in order to obtain a sample of 300 patients completing the Investigation, a total of 400 patients are planned to be enrolled across 8 sites. Accordingly, each site is expected to enrol approximately 50 patients over a period of 6–8 months (estimate based on the current frequency of Chimaera use as reported by the sites during the feasibility phase).

9.8 *Enrolment Timepoint*

Each eligible patient able to provide consent personally will be considered enrolled in the Clinical Investigation at the time of signing and dating the informed consent form, in accordance with the procedures for collection described in this Protocol.

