9.11 Medical-Surgical Procedures and Follow-up of the Clinical Investigation

After obtaining informed consent, the physician will include in the study those patients who, at the screening visit (Visit 0), meet all selection criteria. During the screening visit, the Investigator will also collect demographic data and the patient's medical history.

Enrolled patients, as would also occur if they chose not to participate in the present Investigation, will undergo the surgical procedure (Visit 1) required for the application of the investigational medical device (Chimaera), which marks the beginning of the treatment period.

Following the surgery, the patient will attend five subsequent visits. The first three visits after the surgical procedure are part of the treatment period and are:

- the visit performed at hospital discharge (Visit 2), which, unless complications occur, will take place within 10 days after the date of surgery. During this visit, the physician will perform routine assessments to confirm that the operation and postoperative course have proceeded appropriately;
- the following two visits (Visits 3 and 4), were conducted at 1 month and 3 months after the date of surgery, respectively. These visits conclude the treatment period which, in the absence of complications, is expected to be within 8–12 weeks from the date of surgery, with the consolidation of the treated proximal femoral fracture. Healing will be assessed by the Investigator through radiographic evaluation, performing a qualitative assessment of bone density at the fracture site and the alignment of the bone fragments. Starting from Visit 4 and at all subsequent visits, the Investigator will also complete the Bowers & Parker functional score (efficacy measure) to assess the patient's functional recovery.

For these patients, device removal is not planned unless required due to serious adverse events necessitating a second surgical procedure to complete the treatment of the fracture (safety measure). Once the treatment period is concluded, the follow-up period begins, during which two visits will be conducted (Visits 5 and 6), respectively at 6 months and 1 year after the date of surgery. During these visits, clinical data will be collected to monitor the progression of fracture consolidation, the patient's functional recovery, and the occurrence of any medium-term adverse events.

[figure not shown]

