9.12 Patient treatment schedule

9.13 Table of procedures applicable to each visit

PERIOD		ENROLMENT	TREATMENT				FOLLOW-UP	
VISIT	Number	Visit 0	Visit 1	Visit 2	Visit 3	Visit 4	Visit 5	Visit 6
	Type	Selection	Surgery	Discharge	1° Follow up	2° Follow up	3° Follow up	4° Follow up
	Window	Day 0 ± 1 week	Day 0	Day 5 ± 5 days	Month 1 ± 1 week	Month 3 ± 1 week	Month 6 ± 1 week	Month 12 ± 1 Month
Informed Consent		x						
Verification of Selection Criteria		x	x	x	x	x	x	x
Demographics		x						
Medical History		x						
Radiographic Examination		x	x			x		
Device Implantation			x					
Parker score						x	x	x
Safety Measures			x	x	x	x	x	x

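### The selection-criteria check repeated at Visits 2 to 6 (9.13), with the open-ended criteria cause in 9.15, can end follow-up after a peri-implant fracture or reoperation, against 9.6, 9.10 and 9.11

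*Combined protocol and SAP*

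**What the plan says.** In the 9.13 table the row "Verification of Selection Criteria" is marked at all seven visits, 0 to 6. Section 9.15 lists the causes for which a patient who misses the last visit counts as prematurely discontinued. One of them is that "one of the inclusion criteria will be dropped or an exclusion criterion will occur". It is not limited to the time before or during surgery.

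The exclusions in 9.6.2 include a diaphyseal or distal femoral fracture, multiple fractures, and the case where "he/she is undergoing surgery to address the sequelae of a previously treated fracture". One further exclusion acts as late as the operation itself: a decision to use the long nail or fixed-length screws.

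Other sections point the other way:

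- 9.6: "Patients who meet all of the following inclusion criteria and none of the exclusion criteria will qualify for enrolment in this Clinical Investigation".
- 9.11: the physician includes patients who, "at the screening visit (Visit 0), meet all selection criteria".
- 9.10: participation lasts 12 months for each patient.
- 9.4: the primary event is that the patient "will have to undergo a second operation to continue with the treatment of the proximal femur fracture", within 6 months and because of a device-related serious adverse event. Section 9.11 likewise treats the second surgery as the safety measure and does not say that follow-up ends there.

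Section 9.16 says that data of discontinued and replaced patients are also collected, stored and analysed. Sections 9.14 to 9.16 make a patient discontinued before the Month 3 visit non-evaluable and, during recruitment, replaceable at the investigator's discretion.

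**The concern.** Some events that this safety study exists to record can also be read as newly met exclusion criteria. Section 2 names peri-implant fracture among the serious complications that require reoperation. If it extends to the shaft, it literally meets the diaphyseal exclusion. A reoperation can be read as surgery for sequelae, and a later second fracture as multiple fractures. A site that applies the Visit 2 to 6 check together with 9.15 could therefore close such a patient's follow-up.

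Three things would be at stake:

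- Adverse events and Bowers & Parker scores after the event.
- Evaluable status, if the event falls before Month 3.
- The rest of the 6-month primary window, for a new fracture before Month 6 that is not itself a primary event.

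The missing data would not be a random subset. After a reoperation or peri-implant fracture the loss is tied to device failure; after an unrelated second fracture it is tied to frailty. Both would make the later descriptive results look somewhat better than they are.

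**Working it through.** **The text.** The table has seven visits and seven marks in the row, so a shifted column in the extracted text does not explain it. A check at Visit 1 is consistent with 9.6.2, because one exclusion is decided intraoperatively. A check after Visit 1 can also be needed where consent is deferred under 4.3. Neither explains a routine check at Visits 2 to 6 for everyone. The conflict therefore lies between those later marks plus the 9.15 cause on one side, and 9.6, 9.10 and 9.11 on the other.

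**The plan's own figures.** The plan gives no figure for this point. The two used here as inputs reproduce: 300/(1 − 0.25) = 400 enrolled, and 15 events in 250 (6%) gives an exact two-sided 95% upper limit of 9.703%, as in section 18.

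**Inputs from the documents.** 400 patients (9.7); a primary-event rate of no more than 6% (18); scores at Months 3, 6 and 12 (9.13); 12 months per patient (9.10); 1-year mortality of up to 36% (9.14).

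**Ceiling: every primary-event patient stops at the event.**

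- Patients: 0.06 × 400 = 24.
- Scores scheduled: 3 × 400 = 1,200. Lost: 24 × 2 = 48 (event between Months 3 and 6) to 24 × 3 = 72 (event before Month 3), or 4% to 6%.
- Patient-months planned: 400 × 12 = 4,800. Lost: 24 × 6 = 144 to 24 × 12 = 288, or 3% to 6%.
- Section 9.5 also names a Month 1 score. With it, 1,600 are scheduled and 48 to 96 are lost (3% to 6%).

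**Partial application.** If a share q of 25% to 50% of event patients is discontinued (assumption), 6 to 12 patients lose 6 × 2 = 12 to 12 × 3 = 36 scores.

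**Deaths.** If 36% of event patients would have died anyway and are removed from all visits, the ceiling falls to 48 × 0.64 = 31 to 72 × 0.64 = 46 scores, and the partial case to 12 × 0.64 = 8 to 36 × 0.64 = 23. The scheduled totals above ignore deaths and the planned 25% withdrawal.

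**Shift in the mean mobility score at Month 6 or 12.** Let p be the event rate and d the number of points by which event patients score worse (assumption: 1 to 3). The event share among those observed is p(1 − q)/(1 − pq), so the mean is too favourable by

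shift = d × p × q × (1 − p)/(1 − pq).

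| p | q | d = 1 | d = 3 |
|---|---|---|---|
| 6% | 25% | 0.014 | 0.043 |
| 6% | 50% | 0.029 | 0.087 |
| 6% | 100% | 0.060 | 0.180 |

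At p = 3%, the low end of the literature range in section 18, the range for q of 25% to 50% is about 0.007 (q = 25%, d = 1) to 0.044 (q = 50%, d = 3).

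New fractures that are not primary events, and reoperations that are not device-related or come after Month 6, are not counted. The documents give no rate for them.

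**The case against.** The case against is substantial, and several stronger readings fail on it.

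- *The check fails for every patient after surgery.* A reader might infer this from the requirement in 9.6.1 that "he/she has been diagnosed with a stable or unstable fracture in the pectrochanteric, intertrochanteric, or subtrochanteric region of the femur, not previously treated". The phrase describes the fracture at diagnosis, which surgery does not change. The documents do not support the inference.
- *Section 9.15 orders discontinuation.* It lists causes for missing the last visit. It permits an end of follow-up and does not clearly require one.
- *Each site is left to decide alone.* The sponsor trains every investigator before the first patient (4), must be told of discontinuations (9.15), and intends to monitor all selection-criteria, endpoint and adverse-event data (10). Divergence between sites is possible but not unsupervised.
- *Nothing says that observation continues.* Section 9.10 sets 12 months for each patient, and 9.11 schedules Visits 5 and 6 with no exception for reoperated patients. The schedule in 9.12 cannot be seen in the text available. What can be said is that 9.13 and 9.15 conflict with these sections.
- *A reoperation need not be surgery for sequelae.* Sections 9.4 and 9.11 place it within the same treatment, and the separate serious-adverse-event cause in 9.15 is narrower: it asks for an unacceptable risk that also stops treatment from continuing. This has force, so the reoperation trigger is arguable. The diaphyseal exclusion is the clearer literal case.

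The later check also has a plausible purpose: it could detect entry into another study or use of a non-permitted device. That purpose can be met in another way. The objection that the effect is small is correct.

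**Conclusion.** The conflict is real and should be resolved by a wording change; confidence is moderate. If 9.13 and 9.15 are followed literally, follow-up can stop after a peri-implant diaphyseal fracture and arguably after a reoperation or second fracture. Section 9.16 cannot recover data that were never collected.

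The effect is small. About 24 of 400 patients are concerned if the primary-event rate reaches 6%, fewer if it is lower. The shift in mean mobility is about 0.01 to 0.09 points on a 10-point item, and 0.06 to 0.18 if every event patient were discontinued. These figures rest on the assumed discontinued share and score difference, and they concern a descriptive secondary endpoint with no threshold.

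A reader might infer that the primary percentage itself is deflated. If 9 of 18 reoperated patients were left out and replaced, 9/300 = 3.0% would be reported in place of 18/300 = 6.0%. The documents do not support that: the reoperation has already been recorded, and 9.16 keeps discontinued and replaced patients in the analysis. The primary percentage is largely unaffected. The exception is the unobserved remainder of the 6-month window after a new fracture that is not itself a primary event, which cannot be sized from the documents.

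**What to change.** - **9.13:** mark the selection-criteria check at Visits 0 and 1 only, plus the time of consent for patients who consent later under 4.3.
- **9.15:** limit the criteria cause to criteria not met at entry or at surgery, including the intraoperative exclusion. State that a reoperation or new fracture does not by itself end data collection, which continues to Month 12 unless another listed cause applies.
- **Section 14:** record later changes, such as joining another study or use of a non-permitted device, as deviations.
- **9.15 against 9.11:** reconcile the serious-adverse-event and lack-of-response causes with the description of a second surgery, so that stopping treatment and stopping observation are distinguished. This should change no clinical rule.

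The cost is protocol and eCRF wording, and keeping a few contacts that are already scheduled; 9.5 allows the scale to be completed by telephone. The downside is that the routine later check of criteria that can change is replaced by the deviation log.

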9.16 Patient replacement

Upon notification to the Sponsor, no later than the study recruitment period, non-evaluable patients, at the discretion of the Investigator, may be replaced with a patient who will be assigned a new and unique identification code.

Considering the high percentage of withdrawal usually found with this type of patient, this procedure has the sole purpose of increasing the probability of reaching the expected sample size in terms of evaluable patients. It is understood that the Sponsor will also collect, store and analyze data from prematurely discontinued and replaced patients.

10 Clinical investigation monitoring plan

In order to ensure the proper conduct of the study and the correct recording of study data, at least the following monitoring visits will be planned:

- study start visit;
- two monitoring visits during the active conduct phase of the study;
- Closing visit of the study.

It is understood that, if necessary, for example if numerous deviations from this Protocol occur on a Site,

the Sponsor reserves the right to carry out additional monitoring visits during the live phase of the study.

Prior to each visit, the monitor will contact the Investigator to check availability and schedule the date of the visit, after which they will send a written confirmation specifying the purpose of the visit and any documents to be made available.

On each visit, the monitor must:

- check the updating of the study documentation;
- verify that the Clinical Investigation is conducted and that the data are produced, recorded and communicated in accordance with this Protocol, the Code of Good Clinical Practice – GCP and the applicable legislation;
- verify the correctness of the data entered in the data collection form towards the source data;
- implement any corrective actions.

Note:

The Sponsor intends to monitor the totality of data reported in the informed consent forms, inclusion and exclusion criteria, variables related to study endpoints, and all information regarding serious or non-serious adverse events. If deemed appropriate and necessary, the other data from the study may also be monitored.

11 Clinical Investigation Documentation

During the study initiation visit, the monitor will provide the Investigator responsible for the clinical investigation with a file containing all the paper documentation necessary for the management of the study, namely:

- study protocol with related Synopsis and appendices;
- copy of the approval of the Ethics Committee of reference;
- an original copy of the signed and approved economic agreement;
- list of participating centers;
- information regarding the medical device under observation (Instructions for use and surgical technique);
- certification relating to the CE marking of the device;
- patient information sheet and consent collection form;
- information letter for the attending physician;
- Adverse event reporting form;
- a copy of the data collection form;
- the eCRF access credentials and the platform user manuals.

Note:

The monitor will also deliver an electronic copy, non-modifiable, of all the study documentation for consultation and possible printing according to the needs of the Investigator.

As required by Good Clinical Practice guidelines:

- in order to prevent accidental or premature destruction of study documents, it will be the responsibility of the Investigator to keep the file in a secure environment with controlled access;
- for the entire duration of the clinical investigation, the study documentation must be updated and made available during the monitoring visits;
- the documentation relating to the study should be kept for the longest possible duration and, at least, for 7 years after the completion or conclusion of the Survey.

In the event that the Investigator relies on a third party for the preservation of the documents, he shall inform the Sponsor of the place of storage and the procedure for transferring the file.

12 Data management

No later than the study start visit, the Sponsor will provide an electronic data collection system (eCRF), called *Symphony*, free of charge, on which all data from this Clinical Investigation will be collected.

Symphony is an EDC (*Electronic Data Capture*) solution developed and validated by Arithmos Srl, which is an ISO 9001 and ISO 27001 certified company. *Symphony* therefore has an Information Security Management System in line with international regulatory standards and ensures compliance with regulations by monitoring and archiving the *audit history* directly on the platform.

For more details contact:

ARITHMOS Srl

[name]

[contact]

[contact]

[contact]

No later than the study initiation visit, the Sponsor will provide the Investigators with the necessary training for the correct use of *Symphony*. Furthermore, if necessary, for the entire duration of the Investigation, the Sponsor will maintain a free *help desk* service to support the Investigator.

Each Investigator will be able to access *Symphony* via the internet with private credentials and will only have visibility of the data relating to the patients recruited in their Center. The Investigator assumes responsibility for ensuring that data is entered into the eCRF in a timely manner, i.e., within 2 calendar weeks of the date of the visit.

The processing of clinical data collected through this Clinical Survey will be processed anonymously by the Sponsor in compliance with European data protection legislation, i.e. the General Data Protection Regulation no. 2016/679 (*General Data Protection Regulation* or GDPR).

13 Quality Assurance

In order to ensure the correct conduct of the Clinical Investigation in accordance with *Good Clinical Practice*, the UNI EN ISO 14155:2012 Standard and in accordance with the provisions of this Protocol, the Sponsor:

- during the live phase of the Investigation, it provided for a monitoring plan (described above);
- moreover, if necessary, both during and after the live phase of the Investigation, the Quality Assurance department of the Promoter (as well as national or international regulatory authorities) may perform an audit at the Sites with at least 15 days' notice.

14 Deviations from the clinical evaluation plan

All deviations from this Protocol, detected by the monitor during visits to the Center or spontaneously reported by the Investigator, will be recorded by the Sponsor and stored among the data related to the study.

Each deviation, both borne by the Investigator and the *non-compliant* patient, will be analyzed by the Sponsor and classified as a major or minor deviation. Following this assessment, the Promoter will put in place the corrective actions envisaged by GCP to prevent the deviation from happening again and, if necessary, promptly inform all Investigators and their Ethics Committees.

In addition, at the end of the clinical investigation, the list of deviations will be analyzed to verify any impairment in the interpretation of the results affected by the deviations.

15 Amendments to the clinical evaluation plan

In the event that amendments to this Protocol are necessary, the Promoter:

- classify the nature of the amendments as substantive or non-substantive;
- modify the Protocol and the study documentation affected by the amendments by keeping track of the changes made;
- in the case of non-substantial amendments, for information, it will promptly notify the participating Sites and the related Ethics Committees in writing by sending a copy of the amended documents;
- in the case of substantial amendments, it will suspend the clinical investigation until a new favourable opinion is issued by the Ethics committees involved.

16 Early termination and suspension of clinical evaluation

Early termination occurs when a clinical trial is definitively stopped earlier than planned, i.e., before the end-of-study visit for each Center. The suspension is intended as a temporary interruption which, only following corrective actions and a new assessment and approval by the Ethics Committees involved, can be resumed.

Both the Sponsor and the Investigator reserve the right to interrupt or suspend the Investigation at any time for serious and documented reasons, such as, but not limited to:

- following the emergence of new scientific evidence, or following an interim analysis, or following notifications of *complaints* or the occurrence of an unexpected serious adverse reaction, the continuation of the Investigation constitutes an unacceptable risk for patients;
- clear lack of treatment effect in a significant number of patients due to causes directly attributable to the medical device observed;
- difficulty in enrolling a sufficient number of participants in a reasonable time;
- excessive number of patients withdrawn prematurely and not assessable.

It is understood that:

- any suspension or early termination of the Investigation will be promptly communicated to all enrolled patients including those who have completed the study, to all Investigators and their Ethics Committees, as well as to the competent authority with which the Investigation will be registered;
- upon the occurrence of the early termination of the Investigation, the Promoter will pay the fees accrued up to that moment to the entity with which it has entered into the economic agreement.

17 Adverse events

Foreseeable adverse events from the use of *Chimaera*, as identified by the risk analysis carried out on the product at the design stage, are described in the "POSSIBLE SIDE EFFECTS" section of the package insert of the device (http://abs.orthofix.it/db/resources/PQ_HFN.pdf) in the section.

This clinical investigation is observational and therefore does not involve additional risks for patients and investigators.

Definitions:

- An AE is any unwanted experience associated with the use of the device in a patient.
- An AE is described as a serious AE when the patient, due to that AE:
 - dies;
 - suffers a potentially fatal event;
 - undergoes a prolongation of hospitalization;
 - he undergoes a second hospitalization;
 - reports a permanent disability
 - Reports a birth defect.

Adverse events and effects that will occur during the study will be classified and reported to the Sponsor through the appropriate form provided with the study documentation. The Investigator will be obliged to notify the Sponsor of a serious adverse event within 24 hours of becoming aware of it.

In compliance with the reference legislation (art. 9 of Legislative Decree 46/97 and MEDDEV 2.12.1) moreover, through the use of the ministerial forms, the Investigator and the Sponsor will report to the Ministry of Health all accidents that will occur during the use of the medical device subject to this study by means of a specific report to office V of the DGDMF, as well as to the local EC.

18 Statistics

For this clinical investigation, there are no statistical hypotheses to be tested or direct comparisons with other devices clinically equivalent to the *Chimaera*, so no threshold has been defined to be considered safe and effective.

However, for the sole purpose of recruiting enough patients to be able to consider the data collected for the *primary endpoint* (safety measure of response to treatment) reliable compared to the data reported in the literature, a sample sizing calculation was still performed.

For Chimaera-equivalent devices, the proportion of patients who underwent a second surgery (due to serious device-related adverse events and/or due to device failure) in the literature is reported to be between 3% and 10% depending on the study considered. A sample size calculation was then performed in order to limit the upper limit of the 95% confidence interval of the proportion of patients with second surgery to below 10%.

The following table shows the number of patients and the upper limit of the confidence interval for different possible values of the percentage of the primary *endpoint* (calculations were made using the statistical method of the exact binomial):

Percentage of patients with second intervention	Upper limit of the 95% confidence interval	Number of patients observed
3%	8.518%	100
4%	9.926%	100
5%	9.614%	160
6%	9.703%	250
7%	9.958%	400

Based on the frequencies of serious device-related adverse events and/or device failures received by Orthofix Srl through the passive medical device vigilance system since the device was placed on the market, the expected percentage for the primary *endpoint* is no more than 6%. Therefore, the expected enrollment of 400 patients that will potentially allow us to obtain a sample of 300 evaluable patients is considered adequate for the type and objectives of the present clinical investigation.

The clinical data collected during this Clinical Survey will be analyzed through descriptive statistics:

- the *primary endpoint* will be presented as a percentage value and the corresponding 95% confidence interval;
- the *secondary endpoint* (Bowers & Parker functional score) and other radiographic parameters will be presented via quantitative descriptive statistics (mean, standard deviation, median, minimum, maximum, 95% confidence interval).

During the present Clinical Investigation, if necessary, an interim statistical analysis of the collected data could be carried out, e.g. when all patients have completed the third post-operative check-up (expected within 6 months from the date of operation).

The clinical data obtained from this Clinical Investigation will be used to complete the evaluation of the clinical performance and safety of the *Chimaera* in order to confirm that the device can be considered

effective and safe as assumed under development based on pre-clinical evaluations carried out for obtaining the CE mark.

19 Dissemination of results

The Investigators and the Sponsor undertake to keep the clinical data collected through this Clinical Investigation confidential and confidential until the information is made public in anonymized form by the Sponsor at the end of the Investigation.

Within six months of the last visit to the closure of the Site, the Sponsor assumes responsibility for making the data of the Survey public through the preparation of the final clinical report, containing the aggregated and analysed data of all the Sites, which will be sent to all the Investigators, the Ethics Committees involved and the Competent Authority.

In addition, within 6 months of the finalization of the final clinical report, the Sponsor reserves the right to publish a manuscript containing the aggregated and anonymized data of the multicenter.

At the end of the Survey, the Sponsor will make the results of the patients enrolled in the Site available for publication to each Site.

The Sponsor reserves the right to present the results of this study at scientific meetings or to present these data also to national and international authorities. Furthermore, the Sponsor recognizes the right and interest of all participating Investigators to scientifically publish or disseminate at congresses and meetings the results obtained from this Clinical Investigation.

20 Data Publication Policy

The Sponsor undertakes to share with all Investigators for knowledge and review any preliminary version of the multicenter manuscript before publication.

Any publication by the Investigator may only take place after any multicentre publication by the Sponsor. It is understood that:

- the Investigator may initiate a publication prior to any multicenter publication made by the Sponsor only with the written consent of the Sponsor;
- where no publication has been initiated by the Sponsor within six months of the finalization of the final clinical report, the Investigator will be free to publish the results obtained in his/her Center without the written consent of the Sponsor.

Prior to any publication or presentation of the results, the Investigators undertake to send in due time (in any case not less than 30 days prior to publication or submission) the manuscript/abstract/presentation to the Sponsor for review and approval. The Promoter undertakes to return a revision within 15 days from the date of receipt of the draft.

It is understood that the Promoter's review is aimed at ensuring the correct reprocessing and presentation of the results of the Survey. Changes proposed by the Promoter shall not in any way interfere with the scientific nature and content of the publication.

